3.2.3. Patient risk factors and patient level analysis

A prespecified patient level analysis will be undertaken including all high-risk individuals with data in a standard of care hospital, and all high-risk individuals in an intervention arm who can be presumed to be exposed to the intervention (definition 1: poster and one other intervention on day 0 and day 1; definition 2: any 2 interventions on day 0 and day 1). The relative risk of experiencing the primary (secondary) outcome by exposure to intervention (as defined above) will be estimated in stratified models for the following individual characteristics:

- I. age (years)
- II. ASA status (1-5)
- III. surgical procedure category (Gynaecologic, Obstetric, Neuro, ENT, Orthopaedic, Plastics and Breast, Urology, Gastrointestinal and Hepatobiliary, Cardiothoracics, Other)
- IV. indication for surgery (non-communicable disease, caesarean section, trauma, infection)
- V. urgency of surgery (elective, urgent, emergent)
- VI. severity of surgery (minor, intermediate, major)

This concludes the pre-specified analyses for ASOS-2. Further exploration of the data will take place.

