6.4. Trial intervention

The intervention arm to which each participating site is randomised will be offered to all eligible surgical patients for the duration of the trial.

Intervention arm

Participating sites which have been randomised to increased surveillance will need to provide increased surveillance to surgical patients with a predicted increased

postoperative risk as determined by the ASOS Surgical Risk Calculator⁹ stratification tool (also available at www.asos.org.za). Increased postoperative surveillance can include any of the following; i) admission to a higher care ward than had been planned at the time of surgery, ii) an increase in the frequency of nursing observations in the postoperative period, iii) ensuring that the patient is assigned to a bed in view of the nursing station, and not in a remote location in the postoperative ward, or iv) allowing family members to stay with the patient in the ward in the postoperative period. The nature of the offered increased postoperative surveillance will be left to the discretion of the healthcare workers and the participating sites. However, all sites will be encouraged to include more than one of the increased postoperative surveillance intervention. The healthcare providers will also receive information on the leading causes of postoperative mortality in African surgical patients as documented in ASOS; surgical site infections, bloodstream infection and acute respiratory distress syndrome, pneumonia, acute kidney injury, postoperative bleeding, and cardiac arrest.⁸ This will be known as the 'Postoperative surveillance bedside guide' and will be placed at the bedside of every patient flagged as high-risk by the ASOS Surgical Risk Calculator.⁹ This should be placed in a visible position at the patient's bedside e.g. posted on the wall above the patient's bed.

Control arm

Participating sites randomised to the control arm will provide usual postoperative care to patients. The care will be left to the discretion of the healthcare providers.

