7.3. Secondary studies

The use of the ASOS-2 Trial data for secondary studies will be encouraged.

During the conduct of the ASOS-2 trial we will perform a concurrent process evaluation to gain insight into the implementation process. The process evaluation aims to:

1. Measure protocol compliance (fidelity of implementation)
2. Identify factors that influence success of implementation
3. Verify specified process steps that form part of the implementation of the protocol and logical framework of the trial
4. Generate contextual information about the trial setting

The questions asked by the process evaluation are:

1. Which factors determined fidelity of implementation at the local hospital level?
2. How did implementation of the intervention affect patient care?
3. Why does the intervention produce (or fail to produce) a change in patient morbidity and mortality?

The measurement tools used for the process evaluation are:

1. The post-education, REDCap based, online test
2. The individual participant case report form (CRF),
3. An online database, called the screening log, which is a REDCap application for participating hospitals to record the number of eligible patients daily,
4. Research fellows will perform selected site visits in order to verify specified process steps and perform structured interviews with a sample of stakeholders,
5. Telephonic structured interviews with a sample of stakeholders that cannot be reached by the two research fellows
6. A post-trial, semi-quantitative, REDCap based, online questionnaire built around the key components identified in the structured interviews and the pilot trial

Each member of the local hospital investigator team will be asked to complete the post-education online test prior to patient recruitment. The online test comprises eight short multiple-choice questions which checks comprehension of the key points from the education material.

The individual participant CRF (appendix 3) captures information that allows checking accuracy of risk stratification, fidelity of implementation, and differences in patient experience between non-high risk patients in the two arms.

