4. Radiological or echocardiographic evidence of new loss of viable myocardium or new regional wall motion abnormality
5. Identification of an intra-coronary thrombus at angiography or autopsy

Pulmonary embolism (PE)

A new blood clot or thrombus within the pulmonary arterial system.

Guidance: Appropriate diagnostic tests include scintigraphy and CT angiography. Plasma D-dimer measurement is not recommended as a diagnostic test in the first three weeks following surgery.

Stroke

Embolic, thrombotic, or haemorrhagic cerebral event with persistent residual motor, sensory, or cognitive dysfunction (e.g. hemiplegia, hemiparesis, aphasia, sensory deficit, impaired memory).

Hospital resource use after surgery

We will collect some basic data to describe the treatment resources patients received after surgery.

Critical care admission to treat postoperative complications:

Postoperative complications requiring admission to critical care to treat the postoperative complications or provide critical care support necessitated by the severity of the postoperative complications.

Days in hospital after surgery: Total number of days in hospital after surgery.

Status at hospital discharge or 30th postoperative in-hospital day: The survival status of the patient at hospital discharge, or at the 30 in-hospital day (if the patient had not yet been discharged following surgery). The study is censored at the 30th in hospital postoperative day.

Reference

Appendix 2

African Surgical OutcomeS-2 (ASOS-2) Trial: Hospital 'broadcasting' signage

IMPORTANT PATIENT INFORMATION

A research study is being conducted atHospital.

The research is being done by Dr from the Department of

Why is this research study being done?

To understand if increasing monitoring following surgery, makes surgery safer.

Why are we telling you about this study?

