Higher care ward No YesIncreased nursing observations No YesAssigned a bed in view of nurses' station No YesFamily with patient in ward No YesSevere complications (tick all that apply): Superficial or deep surgical site, or body cavity infection N Y Postop day Bloodstream infection or ARDS N Y Postop day Pneumonia N Y Postop day Urinary tract or AKI N Y Postop day Postoperative bleed N Y Postop day Cardiac arrest N Y Postop day Other severe complication N Y Postop day Days in hospital after surgery Status at hospital discharge or 30th postoperative in-hospital day: Alive & still in hospital Dead Alive & discharged → if alive and discharged, was patient transferred to another facility for higher care? Yes NoIf deceased, photo of clinical note of death uploaded: Yes CRF completed and verified by..... on dd/mm/2019ASOS-2 unique patient ID

ASOS-2 Trial CRF v4 (Control arm)

Patient name: _____

DOB d m y y y Patient hospital number : _____ ASOS-2 unique patient ID

African Surgical OutcomeS-2 (ASOS-2) Trial: Case Record Form (CRF) (Intervention arm)

Age years (<30 points; 0 points/ 30-69 years; 1 point/ ≥70 years; 3 points) Sex M F

ASA I (0 points) II (2 points) III (5 points) IV (8 points) V (8 points)

Chronic co-morbid disease (tick all that apply): Hypertension HIV / AIDS Diabetes mellitus COPD / Asthma

Surgical procedure category (select single most appropriate): Gynaecology (minus 1 point) Obstetrics (minus 1 point)
 Orthopaedic (0 points) Ear, nose and throat (3 points) Plastics or breast (1 point) Urology (2 points)
 Neurosurgery (4 points) Gastro-intestinal or Hepato-biliary (3 points) Cardiothoracic/ vascular (3 points) Other (0 points)

Indication for surgery:
 Non-communicable disease (0 points) Caesarean section (minus 2 points) Trauma (1 point) Infection (2 points)

Urgency of surgery: Elective (0 points) Urgent (3 points) Emergency (4 points)

Severity of surgery: Minor (0 points) Intermediate (2 points) Major (4 points)

Start of surgery time (24h) & date: h h : m m d d m m 2 0 1 9

ASOS Surgical Risk Score points per risk factor:
 Age + ASA + Surgical procedure category + Indication for surgery + Urgency surgery + Severity surgery = points

Time that the ASOS Surgical Risk Score was calculated: Pre-op Intra-op Immediately post-op

Predicted ASOS Risk Score: Not high-risk patient (<10 points) High-risk patient (≥10 points)

Postoperative Follow Up

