Not high-risk patient: (Indicate postoperative care given): Higher care ward No Yes Increased nursing observations No Yes
Assigned a bed in view of nurses' station No Yes Family with patient in ward No Yes

 High-risk patient: (Indicate all postop surveillance)	Day 0	Day 1	Day 2	Day 3	Day 4+
Higher care ward	 No  Yes				
Increased nursing observations	 No  Yes				
Assigned a bed in view of nurses' station	 No  Yes				
Family with patient in ward	 No  Yes				
'Postoperative surveillance bedside guide' at the patient's bedside?	 No  Yes				

Severe complications (tick all that apply): Superficial or deep surgical site, or body cavity infection N Y Postop day
Bloodstream infection or ARDS N Y Postop day Pneumonia N Y Postop day
Urinary tract or AKI N Y Postop day Postoperative bleed N Y Postop day
Cardiac arrest N Y Postop day Other severe complication N Y Postop day

Days in hospital after surgery

Status at hospital discharge or 30th postoperative in-hospital day: Alive & still in hospital Dead
 Alive & discharged → if alive and discharged, was patient transferred to another facility for higher care? Yes No
If deceased, photo of clinical note of death uploaded Yes CRF completed and verified by..... on dd/mm/2019

ASOS-2 unique patient ID ASOS-2 Trial CRF v4 (Intervention arm)

Patient name: _____ DOB d d m m y y y y

Patient hospital number : _____ ASOS-2 unique patient ID

Appendix 4

ASOS-2 Surgical Risk Calculator Score Card

The ASOS Surgical Risk Calculator Score card

The ASOS Surgical Risk Score is used to identify patients requiring 'increased postoperative surveillance'

How to calculate the ASOS Surgical Risk Score:

1. Calculate score before surgery using the table below
2. ASOS Surgical Risk Score = Age (points) + ASA (points) + Surgery timing (points) + Surgery severity (points) + Indication for surgery (points) + Surgery (points)
3. High-risk patients have ASOS Surgical Risk Score ≥ 10 points
4. A high-risk patient has an ASOS Surgical Risk Score ≥ 10 points
5. If ≥ 10 points, then organize 'increased postoperative surveillance' after surgery

Age	Points
18- 29	0
30-69	+1
≥ 70	+3
ASA	
ASA 1	0
ASA 2	+2
ASA 3	+5
ASA 4 and more	+8
Surgery timing	
Elective surgery	0
Urgent surgery	+3

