3.2. Analysis population

Primary analysis will be by modified intention to treat population which includes all patients recruited from randomised hospitals where the hospital reported any patient data. Hospitals that are randomised, but do not submit any patient data will be excluded from the modified intention to treat analysis on the presumption that there is no risk of exposure to the trial intervention. Patients will be analysed in the treatment group to which their hospitals were originally allocated.

Secondary analyses will include two analytic approaches to two per protocol populations. Refer to table: Secondary analyses based on implementation fidelity. In the first per protocol analysis we will compare all patients from hospitals with data in the standard of care arm to all patients from hospitals with data in the intervention arm where the intervention hospital provided the intervention with fidelity to at least 80% of high-risk patients. Patients from hospitals in the intervention arm where the hospital delivered the intervention with fidelity to fewer than 80% of patients will be excluded from this analysis. In the second per protocol analysis we will compare all patients from hospitals with data in the standard of care arm to all patients from hospitals in the top two tertiles of implementation fidelity. Patients from intervention hospitals in the bottom tertile of implementation fidelity will be excluded from this analysis. At the hospital level we will report implementation fidelity as the proportion of high-risk patients who received the intervention with fidelity. We use two definitions for implementation fidelity; i) provision of at least the high-risk bedside guide plus one additional component of the intervention on days 0 and 1 postoperatively and ii) provision of at least 2 components of the intervention on days 0 and days 1 postoperatively, regardless whether the high-risk bedside guide is one of the components.

Secondary analyses based on implementation fidelity		
	Fidelity = High-risk individuals exposed to the bedside guide plus at least 1 additional component of the intervention	Fidelity = High-risk individuals exposed to at least 2 components of the intervention, regardless whether one is the bedside guide
Intervention hospitals where >= 80% of high-risk patients received the intervention with fidelity	Per protocol analysis 1	Per protocol analysis 3

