3.2.2. Sensitivity and subgroup analyses on the effectiveness outcomes

Sensitivity analysis will investigate the potential for unobserved outcomes (transfer out or lost to follow up) to impact primary and secondary effectiveness estimates. Under the same model as the primary (secondary) effectiveness outcomes individuals with unobserved outcomes (lost to follow up) will alternately be assumed to be alive at discharge (censored at thirty days) or to have died in-hospital within 30 days. These estimates and confidence intervals will be plotted along with the primary (secondary) effectiveness estimates.

Primary and secondary endpoints will be analysed under the same model as the primary analysis for the following subgroups treated as stratification variables:

- i) hospital level (primary, secondary, tertiary),
- ii) duration of recruitment (1, 2, 3 or 4 weeks)
- iii) Calendar time (quarters)
- iv) Income category of country (low or middle, according to the World Bank classification in 2020)

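### High-risk patients are the target of the intervention, but no planned analysis compares all of them by allocated arm, and the one high-risk analysis applies an exposure condition to the intervention arm only

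*Combined protocol and SAP*

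**What the plan says.** **Who is targeted.** Under protocol 6.4, intervention sites "will need to provide increased surveillance to surgical patients with a predicted increased" postoperative risk. The score card in Appendix 4 sets the trigger: at 10 points or more, "then organize 'increased postoperative surveillance' after surgery".

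**What is analysed by allocation.** SAP 3.2 (Analysis population) takes all patients, at any risk level, from randomised hospitals that reported data. It adds: "Patients will be analysed in the treatment group to which their hospitals were originally allocated". The four per-protocol analyses drop some intervention hospitals but keep every patient of those that remain, whatever their risk. SAP 3.2.2 says: "Primary and secondary endpoints will be analysed under the same model as the primary analysis for the following subgroups treated as stratification variables". It then lists hospital level, duration of recruitment, calendar quarter and country income. Patient risk group is not listed.

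**The one high-risk analysis.** SAP 3.2.3 takes all high-risk patients with data in control hospitals. From intervention hospitals it takes "all high-risk individuals in an intervention arm who can be presumed to be exposed to the intervention". Both definitions of exposure require components on day 0 and on day 1. Relative risks are then estimated in models stratified by age, ASA class, procedure, indication, urgency and severity. The SAP closes its pre-specified list at that point.

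**Protocol 7.2** mentions the calculator's risk factors only as variables to include in the analysis, not as a high-risk comparison.

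**The concern.** The two sides of the 3.2.3 comparison are selected by different rules. A control patient needs only to be high-risk. An intervention patient must also have had surveillance on two successive days, which is known only after allocation and depends on being alive and in hospital. The benefit of cluster randomisation is therefore lost.

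Three things follow:

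- A high-risk intervention patient who dies on day 0 cannot meet the day-1 condition and is removed. The same death in a control hospital is counted. This favours the intervention.
- A survivor who leaves before day 1 is removed from the intervention side only. This works against the intervention.
- Staff may watch sicker patients more closely, so exposed patients may have a worse prognosis. This also works against the intervention.

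At stake are the only pre-specified estimates in the patients the intervention is meant to help. As written, they could show benefit or harm with no true effect, and no by-allocation high-risk result is planned to set beside them.

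**Working it through.** **1. The plan's own figure.** For 2.0% versus 1.5%, 80% power and two-sided 0.05, a standard two-proportion calculation gives 10,795 patients per arm. The design effect with mean cluster size 100, ICC 0.015 and CV 0.63 (protocol 7.1) is 1 + ((1 + 0.63²) × 100 − 1) × 0.015 = 3.08. That gives 666 clusters against 664 in Table 1, so the figure reproduces. With 664 clusters (33,200 per arm) power is 79.9%. The overall primary analysis is as powered as the plan says.

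**2. Inputs for the bias.** The documents give neither high-risk mortality nor the timing of deaths or discharges. These are assumptions:

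- p, mortality in high-risk patients: 5–10%
- f, share of high-risk deaths before the exposure definition can be met: 5–30%
- g, share of high-risk survivors who leave before day 1: 0–10%

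**3. Formula with no true effect.** Control risk is p. Among retained intervention patients, deaths are p(1 − f) and survivors are (1 − p)(1 − g). So

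RR = [p(1 − f) / (p(1 − f) + (1 − p)(1 − g))] / p,

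which is (1 − f)/(1 − pf) when g = 0. If uptake is unrelated to prognosis it multiplies deaths and survivors alike and cancels. The high-risk share and the ICC do not enter.

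Example with p = 7%, f = 20%, g = 0, and 1,000 high-risk patients per arm: control has 70/1,000 = 7.0%. Intervention loses 14 early deaths, leaving 56/986 = 5.7%. RR = 0.81.

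| f | RR, g = 0, p = 5% to 10% | RR, g = 10%, p = 7% | Break-even exposure ratio, g = 0 |
|---|---|---|---|
| 5% | 0.952–0.955 | 1.051 | 1.05 |
| 10% | 0.905–0.909 | 1.000 | 1.11 |
| 20% | 0.808–0.816 | 0.896 | 1.25 |
| 30% | 0.711–0.722 | 0.790 | 1.43 |

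The last column is 1/(1 − f): how many times as often later deaths would have to be exposed, compared with survivors, to cancel the early-death bias.

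**4. Bias in the alternative.** A by-allocation comparison of all high-risk patients has expected RR 1.00 with no true effect, provided classification does not depend on arm. It may depend on arm. Staff know the allocation, and the intervention CRF (Appendix 3) allows late scoring: "Time that the ASOS Surgical Risk Score was calculated: Pre-op Intra-op Immediately post-op". Suppose 10% more patients, with mortality q of 0.5–1%, cross the cut-off in the intervention arm (assumption). The null RR is (p + 0.10q)/(1.10p). At p = 5–10% this is 0.914–0.927.

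**The case against.** **The objective is overall mortality.** The primary and secondary objectives concern all adult surgical patients, and the plan analyses all of them by allocation. That also captures any shift of care away from lower-risk patients and avoids a subset defined after allocation. This stands as a defence of the primary analysis. It does not justify making the sole high-risk analysis an asymmetric one.

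**The remedy is biased too.** A null RR of 0.91–0.93 from differential scoring is about as far from 1 as the case of 10% early deaths. That is true on those assumptions, and opposing biases in 3.2.3 could happen to cancel. But 3.2.3 depends on the same scoring and adds its own selection; the by-allocation version carries only the scoring problem.

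**The size is assumed.** This stands. The Introduction says 95% of deaths in ASOS were postoperative, which leaves 5% earlier. That figure covers all ASOS patients and says nothing about day 0–1 timing in high-risk patients, so it neither supports nor excludes the larger values.

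**It is labelled as an analysis by exposure, it is stratified, and further exploration is allowed.** The label is fair, and no pooled high-risk estimate is stated. But the asymmetry is present in every stratum, and a by-allocation comparison added later would be post hoc.

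**The control data may not exist.** I could not see the preoperative part of the control-arm CRF. That it holds the score components is inferred: 3.2.3 must identify high-risk controls, and protocol 7.3 says the CRF "captures information that allows checking accuracy of risk stratification".

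**A landmark is a partial repair.** Correct. It makes early deaths and discharges symmetric, but it still compares selected exposed patients with all controls and conditions on survival that treatment may affect.

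**Conclusion.** The concern holds. No pre-specified analysis compares all high-risk patients by allocated arm, and 3.2.3 conditions only the intervention side on surveillance over days 0 and 1. This rests on the text alone and is certain.

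The size and net direction are not. On the stated assumptions the 3.2.3 relative risk with no true effect spans 0.71 to 1.05. With no early live discharge it is about 0.95, 0.91, 0.81 and 0.71–0.72 for 5%, 10%, 20% and 30% early deaths. The last is about as large as the trial's target of 0.75. Selective surveillance of sicker patients could move it further upwards.

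The primary analysis is untouched and remains the answer to the main question. This should be corrected, but it does not threaten the trial's main conclusion.

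**What to change.** Keep the overall primary outcome and analysis. In the SAP:

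1. Add risk group (score 10 or more versus below 10) to the 3.2.2 subgroups, by allocated arm under the primary model, with an arm-by-risk-group interaction test. Recompute the score centrally from the CRF components in the same way in both arms.
2. Make all high-risk patients by allocated arm the main analysis in 3.2.3, with the status of a secondary analysis.
3. Label the exposure-based version exploratory and apply one landmark to both arms: alive and in hospital at the end of day 1. Both CRFs record status at discharge and days in hospital, which Appendix 1 defines as "Total number of days in hospital after surgery". The SAP should state which recorded values count as past the landmark.
4. Report the proportion scoring 10 or more, and the distribution of each score component, by arm.

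The cost is SAP wording and one extra model on data that 3.2.3 already needs. Central recomputation removes arithmetic differences but not differences in how unblinded staff grade ASA class, urgency or severity. Item 4 makes such a shift visible, and the subgroup should be read with that caution.

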Statistical analysis	The primary outcome measure is in-hospital mortality censored at 30 days of randomisation. The analysis will be conducted according to intention-to-treat principles; all participants with a recorded outcome will be analysed according to the treatment group to which they were randomised.
Recruitment start date	May 2019
Recruitment end date	March 2020
Trial duration	Until hospital discharge, censored at 30 days

3. Introduction

The non-cardiac surgical population represents a major global public health burden with approximately 234 million major surgical procedures performed worldwide each year.¹ In unselected non-cardiac surgical patients, reports of early postoperative mortality vary between 2 and 4%,^{2,3} with an annual global mortality of 5 to 10 million. Surgery is a cost-effective intervention,⁴ even in low to middle income countries⁵ and as such it is considered a core component of health.⁶ The Lancet Commission on Global Surgery was established to define safe surgery and develop strategies to ensure the adequate provision of safe surgery.⁷

Recently, the African Surgical Outcomes Study (ASOS) demonstrated, that despite a patient low risk profile and low complication rates, patients in Africa were twice as likely to die following surgery when compared to the global average.⁸ ASOS provides the most comprehensive data on surgical outcomes in Africa, comprising 25 countries, 247 hospitals, and data from over 11 000 patients.⁸ Importantly, 95% of the deaths in ASOS occurred in the postoperative period, suggesting that many lives could be saved by effective surveillance for physiological deterioration amongst the patients who developed complications.⁸ In ASOS, the median number of combined anaesthesia, surgical and obstetric specialists was 0.7 (IQR 0.2-1.9) per 100,000 population,⁸ which is well below the documented inflection point of 20 to 40 specialists per 100,000 population necessary to significantly decrease surgical mortality.⁷

It is likely that a major contributor to the high mortality in ASOS was 'failure to rescue' after a postoperative complication partly due to an inadequacy of sufficient human resources necessary to identify postoperative surgical patients at risk. A potential solution to improving surgical outcomes in Africa is identification of the high-risk surgical patient prior to further physiological deterioration.

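### SAP 3.2.3 applies a day 0 and day 1 exposure rule to the intervention arm only, so early deaths and early discharges leave that arm but stay in control, and the null relative risk need not be 1

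*Combined protocol and SAP*

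**What the plan says.** The patient-level analysis in SAP 3.2.3 defines its two arms differently. Control is described as "including all high-risk individuals with data in a standard of care hospital". The intervention arm is limited to high-risk patients presumed exposed, under "definition 1: poster and one other intervention on day 0 and day 1; definition 2: any 2 interventions on day 0 and day 1". Relative risks are then estimated in models stratified by age, ASA status, procedure category, indication, urgency and severity.

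The outcome is in-hospital death up to 30 days (SAP 2.1), so deaths on day 0 and day 1 count.

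The per-protocol analyses (SAP 3.2, Analysis population) use the same two-day condition to measure hospital fidelity, for example "provision of at least the high-risk bedside guide plus one additional component of the intervention on days 0 and 1 postoperatively". They then remove hospitals from the intervention arm only: "Patients from intervention hospitals in the bottom tertile of implementation fidelity will be excluded from this analysis".

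Protocol 6.4 says the form of surveillance "will be left to the discretion of the healthcare workers and the participating sites". In Appendix 3, the intervention form has a block headed "High-risk patient: (Indicate all postop surveillance" with columns from Day 0 to Day 4+. The part of the control form available for review records each component once, without days. Both forms carry "Days in hospital after surgery Status at hospital discharge or 30th postoperative in-hospital day".

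**The concern.** Meeting the exposure rule requires a patient to survive, and stay in hospital, long enough to be scored on day 1. Applied to one arm, this is immortal time: early deaths are removed from the intervention arm and kept in control, which favours the intervention. Removing early live discharges from that arm takes out survivors and works against it. The SAP sets no landmark, no matching restriction in control, and no rule for scoring day 1 in a patient already dead or discharged.

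Stratifying by six baseline characteristics cannot undo selection on a later event. The sensitivity analysis in SAP 3.2.2 deals with unobserved outcomes, not with this exclusion. Because surveillance is discretionary, who qualifies is also confounded, in an unknown direction.

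This is the only prespecified comparison confined to high-risk patients, the group the intervention targets. Readers will look here for an effect in treated patients, and could not tell how much of any difference came from the entry rule.

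**Working it through.** **The plan's own figures.** SAP 3.2.3 gives none. The simulation below uses the Table 1 design, which reproduces: 2.0% versus 1.5%, two-sided 0.05 and 80% power need 10,795 patients per arm. The design effect is 1 + ((1 + 0.63²) × 100 − 1) × 0.015 = 3.080. Then 10,795 × 3.080 / 100 rounds up to 333 hospitals per arm, 666 in all, against 664 stated. The concern does not depend on this number.

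**Null relative risk, patient level.** Let
- p = mortality in high-risk patients (assumed 10%; 5% and 15% also tried),
- f = share of deaths too early to meet the rule,
- g = share of survivors discharged too early to meet it.

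With no true effect, mortality is p in control. In the filtered intervention arm it is p(1 − f) / [p(1 − f) + (1 − p)(1 − g)]. Dividing by p:

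RR = (1 − f) / (1 − f·p − g·(1 − p)), which equals 1 only when f = g.

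**Anchor for f.** Protocol section 3 reports that "95% of the deaths in ASOS occurred in the postoperative period". About 5% of deaths could therefore never have received postoperative surveillance. Such deaths can be in the dataset, because a form is completed for every eligible patient who has surgery (6.5) and risk is to be scored before surgery (6.8, Appendix 4). The 5% covers all patients, not only high-risk ones, and leaves out deaths soon after surgery. All other values of f and g are assumptions.

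| f | g | Calculation at p = 10% | Null RR |
|---|---|---|---|
| 5% | 0 | 0.95 / 0.995 | 0.95 |
| 10% | 0 | 0.90 / 0.99 | 0.91 |
| 20% | 0 | 0.80 / 0.98 | 0.82 |
| 5% | 5% | 0.95 / 0.95 | 1.00 |
| 5% | 10% | 0.95 / 0.905 | 1.05 |
| 10% | 5% | 0.90 / 0.945 | 0.95 |
| 20% | 5% | 0.80 / 0.935 | 0.86 |

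Taking p as 5% or 15% moves each value by at most 0.01. At f = 30%, g = 0, the RR is 0.70 / 0.97 = 0.72, beyond the planned 0.75.

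**Simulation with no true effect.** 500 runs per scenario; 332 hospitals per arm, mean size 100, CV 0.63, ICC 0.015. Assumed: 15% of patients high-risk, mortality 10% in high-risk and 0.6% in other patients, and hospital delivery drawn from Beta(6, 1.5), Beta(2, 1) or Beta(20, 3).

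| f, g | Patient level (3.2.3) | Per protocol, ≥80% fidelity | Per protocol, top two tertiles |
|---|---|---|---|
| 20%, 0 | 0.81–0.82 | 0.96–0.97 | 0.95–0.99 |
| 10%, 0 | 0.90–0.91 | 0.98 | 0.97–0.99 |
| 5%, 10% | 1.05 | 1.01 | 1.01 |

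The per-protocol bias is much smaller because whole hospitals are kept or dropped. A separate simulation of similar design matched the patient-level results and gave about 0.96 to 1.02 for the per-protocol analyses.

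**After the change.** With the landmark in both arms, and fidelity computed among landmark patients, all simulated RRs were 0.99 to 1.01. In closed form the null RR is 1.00 for any p, f and g, provided early exits do not differ by arm.

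**The case against.** *Size.* The one documented anchor gives 0.95, and 1.00 to 1.05 once 5% to 10% early discharges are added. Under the simulation's inputs each arm has 332 × 100 × 0.15 = 4,980 high-risk patients and about 498 deaths. With about 15 high-risk patients per hospital, the design effect is 1 + ((1 + 0.63²) × 15 − 1) × 0.015 = 1.30. The standard error of log RR is √(1.30 × 2 × 0.9 / 498) = 0.069, so the 95% interval runs from about −13% to +14%. Biases of 0.95 and 0.91 (z about −0.7 and −1.4) lie inside it, and intervals within strata are wider. This stands: at the documented anchor the bias alone is unlikely to reach significance. It still shifts the estimate and its interval.

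*Reading of the rule.* A patient who dies or leaves on day 1 may still qualify if the Day 1 boxes were ticked; only exits before then certainly fail. This stands, but the missing scoring rule is part of the defect.

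*Confounding.* Protocol 7.2 already says the risk-calculator factors will enter the analysis, and they are the same six characteristics. This meets part of the confounding point. It does nothing for early exits.

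*Landmark timing.* Appendix 1 does not say whether the day of surgery counts in days in hospital, and the visible forms show no date of death or discharge. The SAP was added on 19 March 2020, late in recruitment, so a one-day counting error cannot be fully recovered. This weakens the landmark, but not the allocation-based comparison, which needs no exit timing.

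*Control form.* Part of it was not available, so the statements that exposure cannot be mirrored there, and that the score items are on it, rest on what is visible or are unchecked. The asymmetry in the SAP text does not depend on this.

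*Estimand.* An allocation-based analysis answers a different question from an exposure analysis. That is true, so the exposure analysis may be kept alongside it if its entry rule is repaired.

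**Conclusion.** The concern holds. SAP 3.2.3 filters one arm on a condition met only after surgery, and nothing elsewhere in the plan corrects this. The early-death part favours the intervention and the early-discharge part opposes it; they cancel only if the two shares are equal. Over the cases tabulated, the null RR runs from 0.82 to 1.05. The documents support only an early-death share near 5% (RR 0.95 with no early discharges), so neither the net size nor the sign can be fixed in advance. High-risk mortality, the discharge share and the larger early-death shares are assumptions.

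The asymmetry itself is certain. It should be corrected, but it does not threaten the trial's main result: the modified intention-to-treat analysis does not use this rule, and the per-protocol analyses are only slightly affected.

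**What to change.** **Lead change.** Make the high-risk analysis allocation-based: all patients scoring 10 or more, with the score computed from the CRF items by the same algorithm in both arms, comparing intervention with control hospitals under the primary model and stratified by the six listed characteristics.

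**If the exposure analysis is kept as well:**
1. Restrict both arms to high-risk patients alive and in hospital at the end of postoperative day 1. Derive this from days in hospital and final status, and state that the day of surgery is day 0.
2. Adjust for the ASOS risk factors.
3. Report exclusions by arm and reason: died, discharged, not delivered.
4. Label the result non-randomised.

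**Per-protocol analyses.** Compute hospital fidelity only among high-risk patients alive and in hospital through day 1.

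**Cost.** SAP wording and some programming; no new data. The landmark version says nothing about deaths on days 0 and 1, depends on how sites counted days, and does not remove selection of who received surveillance. The allocation-based version has none of these limits.
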